2.2 STUDY DESIGN SPECIFICS

Clinical Assessments

PD cohort

All potential participants will undergo neurological and neuropsychological examination to determine eligibility, categorize MCI status, and provide quantification of neurocognitive functioning and neuropsychiatric symptomatology.

Screening data (see inclusion/exclusion criteria) from eligible enrollees will be also used as part of clinical baseline assessment.

Neurological examination will include the Unified Parkinson's Disease Rating Scale III (UPDRS-III)⁵⁶ and the Clinical Dementia Rating (CDR)⁵⁷ scale. Vitals and a blood sample (10mL) will be collected as part of this examination. Medical history will include an inquiry as to whether the participant is actively dieting.

The neuropsychological examination protocol will consist of a memory measure (i.e., the Hopkins Verbal Learning Test – Revised [HVLT-R]⁵⁸, consisting of Learning, Recall, and Recognition subcomponents), executive functioning measures (i.e., Trail Making Test – A & B⁵⁹, Verbal Fluency [FAS]⁶⁰, Stroop⁶¹), and exploratory measures of cognitive-performance thought potentially sensitive to PD-related pathology (Brief Estimate of Seconds Test [BEST]⁶², Simon Task⁶³). To evaluate sleep disturbance symptomatology,

PROMIS – Sleep Disturbance (SD) and Sleep-related Impairment (SRI) short forms will be administered⁶⁴. To evaluate mood symptomatology, the Hospital Anxiety and Depression Scale (HADS)⁶⁵ will be administered.

Physical assessment is routinely completed at the first and last visit of the community-based exercise program, including rating/timing of ability to complete simple posture and gait tasks, as well as self-reported difficulty with gait initiation. UPDRS-III will also be administered at screening (on-drug), baseline assessment (off-drug), and follow-up assessment (off-drug) Additionally, between enrollment and competition, the patients will wear an actigraph to continuously measure motor activity.

Healthy cohort:

All participants will be administered the Brief Estimate of Seconds Test (BEST) in person or via Microsoft Teams.

Imaging

PD cohort

MRI. Participants will begin with MRI in the morning after their 16-hour dopaminergic washout the night/evening prior. Self-reported total sleep time the night prior will be recorded. They will be free to re-initiate therapy after MRI is complete. The following imaging and angiography sequences will be completed. We will apply our previously-reported 3T methods (16-channel neurovascular coil) with the below 50 min protocol:

- Anatomical imaging. *T*₁-weighted (MPRAGE; spatial resolution=1.0x1.0x1.0mm³; 3D turbo-gradient-echo; TR/TE=8.2/3.7ms), and T₂-weighted (FLAIR; spatial resolution=0.9x1.1x3.0mm³; turbo-inversion-recovery; TR/TI/TE=11000/2800/120ms) imaging, and intracranial (spatial resolution = 0.5x0.8x1.4mm³; 3D gradient echo; TR/TE=23/3.5ms) and extracranial (spatial resolution=0.9x0.9x3.0mm³; 2D gradient echo; TR/TE=18.6/3.2ms) time-of-flight (TOF) MR angiography (MRA).
- Microvascular hemodynamic compliance. A single-shot gradient echo echo-planar-imaging (EPI) scan (TE=30 ms), multiband-factor=3, isotropic spatial resolution=2 mm, SENSE-factor=2.5, and TR=1s will be acquired with whole-brain coverage. The scan will utilize a hypercapnic normoxic (5% CO₂ / 21% O₂ / 74% N₂) stimulus. The stimulus will be administered through a tight-fitting non-rebreathing oxygen facemask from compressed gas cylinders (flow rate=12 L/min) with the following paradigm: 180s normocapnic normoxia / 90s hypercapnia repeated once, followed by 180s normocapnic normoxia. Heart and respiration rate, EtCO₂, and FiO₂ will be recorded.
- CSF flow. 2D-Qflow measurements will be performed in the cerebral aqueduct (Fig. 7). V_{enc}=12 cm/s, spatial resolution = 0.5x0.5x4 mm³, field-of-view = 200x200x4 mm³, and 30 frames per heart cycle. Scan durations vary with heart rate, but are generally 2-4 min. Reproducibility has been determined by repeating the flow measurements in six subjects (Fig. 7). Background correction will be performed with a method previously developed for quantification of blood flow velocity in small perforating arteries⁴.
- Lymphangiography for lymph vessel visualization. 3D turbo-spin-echo with variable refocusing angle sweep=40-110°, driven equilibrium module, dynamic DANTE flip angle sweep=0-8°, TE=600/TR=2500ms, slices=80, spatial resolution=1x1x1mm³. We have shown that this method provides sensitivity to long T_2 slow flow species, such as lymph, and we have evaluated this method for sensitivity to lateralizing lymphedema and MLD therapy²⁶ (Figs. 3,4).

- Susceptibility weighted imaging (SWI) for identification of medullary veins. Whole-brain 3D turbo-gradient-echo (TR/TE₁/②TE=31/7.2/6.2 ms; flip angle=17°) with spatial resolution=0.6x0.6x2 mm³ (slices=130) will be acquired with the same slice angulation as DTI.
- Diffusion tensor imaging (DTI) for perivascular flow determination. Whole-brain 2D spin echo EPI (TR/TE=10000/60 ms) in 32 directions (2 mm isotropic spatial resolution) using sequential acquisitions with b=0 s/mm², b=1000 s/mm², and b=2000 s/mm².
- Spin labeling for cervical LN perfusion. Spin labeling will be performed with an 11-ms hypersecant inversion (labeling) prepulse, followed by an inversion time range of 300 to 2400 ms in 300 ms increments, which will enable blood transit time and perfusion quantification. Other parameters: labeling=STAR; TE=11 ms; spatial resolution=2x2x2 mm3; averages=14.

PET/CT. A single administration of approximately one-time intravenous administration of 555 MBq (15 \pm 1.5 mCi) C11PiB, then a 70-minute dynamic PET/CT acquisition (4 x 15, 8 x 30, 9 x 60, 2 x 180, 10 x 300 second frames frames) will be performed. Images will be reconstructed using an ordered subset Estimate algorithm (4 iterations, 16 subsets, with a post-reconstruction Gaussian filter of 5 mm), and corrected for scatter and attenuation. Images will be co-registered to the high spatial resolution T_1 -weighted image as we have performed previously and a mean cortical:cerebellar SUVr will be calculated as the primary parameter of interest. For exploratory evaluation, we will also record SUVr in bi-temporal, bi-occipital, bi-frontal, and bi-parietal lobes.

Exercise

PD cohort

Patients will undergo an initial evaluation with [name], the Rock Steady Boxing instructor. Each class consists of 60 minutes of intense aerobic exercise. Of note, this class is specifically designed for patients with gait, balance, and motor symptoms common to Parkinson's disease. Individuals with symptoms that preclude safe participation are screened out as part of the program's routine initial evaluation. All components of the class are non-contact, and strictly aerobic in nature. They will receive 20 class credits (over two installments), as the program recommends attempting to attend roughly twice per week. As this is an observational study, participants will not be excluded based on their attendance, though this variable will be monitored to aid in analyses and interpretation. As noted above, a final physical evaluation will also be conducted on their last class.

Follow-up

PD cohort

Clinical and neuroimaging assessments will be conducted within 1 week of completion of the exercise program.

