neurologic examination, from ages 55-80, with and without mild cognitive

impairment (MCI)

Healthy cohort: healthy adults (ages 18-90) without neurological or

psychiatric/developmental pathology.

Phase: Observational

Description of Sites: Vanderbilt University Medical Center

Description of Study

PD cohort: MRI Brain scan, PET/CT Brain scan, Neurological and

Activities:

Neuropsychological exams, continuous Actigraphy, 12-week community-

based exercise program

Healthy cohort: Neuropsychological exam

Study Duration: PD cohort: 36 months

Healthy cohort: 24 months

Participant Duration: PD cohort: 3 months

Healthy cohort: 1 day

Medical Monitor: [name], will act as the independent medical/research

monitor overseeing this study. The research monitor may perform

functions such as observing enrollment procedures for individuals, groups, or units; overseeing study interventions; overseeing data matching, data collection, and analysis. The research monitor shall have authority to stop a research protocol in progress, remove human subjects from the research protocol if necessary, and protect the safety of human subjects until the IRB assesses the monitor's report, and shall have the responsibility to promptly report their observations and findings to the IRB or other

designated official and the HRPO.

Week 0, Day 0

Screening

- Obtain informed consent
- •Obtain history, screen potential participants by inclusion and exclusion criteria

Week 1, Day 1-7

Baseline

- •MRI brain scan
- •PET brain scan
- •Neurological & Neuropsychological exam

Week 2-13, Day 8-91 Interval

- Baseline PT assessment
- •Twice-weekly participation in community-based exercise program
- •Continuous actigraphy & Neurametrix
- •Follow-up PT assessment

Week 14, Day 92-99 End of Study Assessments

- •MRI brain scan
- •PET brain scan
- •Neurological exam, neuropsychological exam, document

Schedule of Activities (SoA) – Assessment Only

| Procedures | Screening Day - 0 | Baseline (VUMC) Day 1-7 | Baseline (RSB; first day) | Interval / Exercise Day 8-91 | Follow-up (RSB; last day) | Follow-up (VUMC) Day 92-99 |
|-------------------------------------------------------------------------------------------|----------------------|----------------------------|---------------------------|---------------------------------|---------------------------|-------------------------------|
| Informed consent | Х | | | | | |
| Demographics / Medical history / Exclusion & Inclusion | х | | | | | |

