2.3 END OF STUDY DEFINITION

PD cohort

A participant is considered to have completed the study if he or she has completed both baseline and follow-up assessment phases of the study, as well as attended at least 1 of the community-based exercise classes.

The end of the study is defined as completion of the last visit or procedure shown in the SoA in the trial globally.

Healthy cohort

A participant is considered to have completed the study if they have completed the BEST.

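### Follow-up on three physical secondary endpoints is set by each patient's own last class, not by a study day, so whether and when it is measured depends on attendance

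*Protocol*

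**What the plan says.** Protocol 1.1 lists the Mini-BESTest, Freezing Gait Questionnaire and 6-minute Walk Test as secondary endpoints. The Schedule of Activities places them in two columns only, "Baseline (RSB; first day" and "Follow-up (RSB; last day". Neither column has a day number, whereas the medical-centre follow-up has Day 92-99. The synopsis timeline puts the follow-up physical assessment somewhere in the Day 8-91 block.

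Protocol 2.2 (Clinical Assessments) says "Physical assessment is routinely completed at the first and last visit of the community-based exercise program". Protocol 2.2 (Exercise) is more specific to the individual: "a final physical evaluation will also be conducted on their last class". The same section says that attendance is monitored but is not a ground for exclusion. Protocol 2.3 defines a completer as someone with both the baseline and follow-up assessment phases who also "attended at least 1 of the community-based exercise classes".

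The SAP does not name these three tests. It does say that every participant gets follow-up whatever the compliance (A.2.1.1), and that compliance is used as a scalar variable so that all patients are retained (B, patient attrition).

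On the class schedule, the synopsis has "Twice-weekly participation in community-based exercise program". Protocol 2.2 has "They will receive 20 class credits (over two installments" and a recommendation of roughly two classes a week. SAP A.2.1.1 has 12 once-weekly classes. Clinical and imaging follow-up is "within 1 week of completion of the exercise program" in Protocol 2.2 and Day 92-99 in the schedule.

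**The concern.** A pre-post change needs a follow-up that happens for reasons unrelated to the exposure. Here the follow-up date is itself a product of attendance. A patient who drifts away has a last class that nobody knew was the last, so no test is arranged. A patient who announces that they are stopping can be tested, but after a short interval. Nothing in either document gives a minimum interval, a fallback date or an adjustment for interval length.

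Three things are at stake:

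- **Mean change.** If low attenders are the ones missing, the observed mean describes the better attenders.
- **Compliance.** SAP A.2.2 and A.3.2 will explore whether compliance relates to change across the assessment modalities. If that is applied to these tests, fewer classes and less elapsed time go together and cannot be separated.
- **Imaging and clinical change.** Protocol 1.1 asks whether imaging response mediates clinical improvement. For these tests the two changes would cover different periods, and the mismatch would vary with attendance.

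**Working it through.** **Inputs.** Exercise interval Day 8-91, baseline imaging Day 1-7 and follow-up imaging Day 92-99 (Protocol 1.1); 20 credits at roughly two per week (Protocol 2.2); 12 weekly classes (SAP A.2.1.1); a minimum of one class (Protocol 2.3). Two assumptions are mine: the first class is on Day 8, and twice-weekly classes alternate gaps of 3 and 4 days.

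**The plan's own figure.** 91 - 8 + 1 = 84 days = 12.0 weeks, which agrees with the stated course.

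**Imaging interval.** Shortest 92 - 7 = 85 days; longest 99 - 1 = 98 days. Attendance plays no part.

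**Physical-test interval.** Day of last class minus day of first class; the gap to the medical-centre visit is 92 (or 99) minus the day of last class.

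| Attendance pattern | Last class | Pre-post interval | Gap to Day 92-99 |
|---|---|---|---|
| 24 classes, two per week | Day 88 | 80 days | 4-11 days |
| 12 classes, one per week (SAP) | Day 85 | 77 days | 7-14 days |
| 20 classes, exactly two per week | Day 74 | 66 days | 18-25 days |
| Stops after 12, two per week | Day 46 | 38 days | 46-53 days |
| Stops after 6 | Day 25 | 17 days | 67-74 days |
| Stops after 2 | Day 11 | 3 days | 81-88 days |
| One class | Day 8 | 0 days | 84-91 days |

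The possible range is 0 to 91 - 8 = 83 days. The interval depends on when the last class falls, not only on the number attended: a patient with few classes spread to Day 91 still has 83 days.

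**With a fixed window.** From a Day 8 baseline, testing in the last scheduled week (Day 85-91) gives 85 - 8 = 77 to 91 - 8 = 83 days. Testing in Day 92-99 gives 84 to 91 days. Either holds whatever the attendance.

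**Class supply.** Twice weekly for 12 weeks is 24 classes against 20 credits. Spread evenly, 20/12 = 1.67 per week. At exactly two per week, 20 credits last 20/2 = 10 weeks: Day 74 by counting classes, or Day 77 (8 + 70 - 1) as the end of the tenth week. The medical-centre visit would then be 92 - 77 = 15 to 99 - 74 = 25 days after the last class.

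**The case against.** Several stronger readings are tempting, and the documents do not support them.

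- **A one-class completer necessarily has a zero interval.** Zero requires both tests on the same day, which nothing prescribes. A missing follow-up is likelier. The instructor's initial evaluation may also precede the first class. Completion requires the follow-up assessment phase, and Protocol 2.3 does not say whether that includes the exercise-site tests, so such a patient may not be a completer. Protocol 3.1 also allows withdrawal for significant non-compliance. All this stands: zero is the lower bound, not the expected case.
- **Full attenders run out of classes early, and follow-up then has two conflicting dates.** A rate of 1.67 per week fits a recommendation of roughly two. If completion of the programme means Day 91, one week later is about Day 92-98, in near agreement with the schedule. Two dates arise only if completion means the patient's own last class. The wording leaves this open, so it needs clarifying but is not a proven contradiction.
- **The planned tests are compromised.** The SAP's specified compliance regression uses DTI-ALPS change, and Hypotheses 3A-3D use cognition and PROMIS scores, all from the fixed medical-centre visit. Only the general statements on compliance and the protocol's mediation objective reach these three tests.

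It can also be argued that the last visit of the programme means its final session for everyone. The wording in Protocol 2.2 on the patient's own last class points the other way, and no date settles it. Even on that reading there is no provision for a patient who has already stopped.

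**Conclusion.** The point holds for three secondary endpoints. As written, the timing rule makes the existence and length of the pre-post interval depend on attendance: 0 to 83 days, against 85 to 98 days for imaging. This works against the SAP's stated aim of following everyone. The range assumes a first class on Day 8 and a last class no later than Day 91. The size of any bias cannot be given, because neither document says how many patients will stop early. DTI-ALPS, SUVr, UPDRS-III, cognition, sleep and mood keep their fixed window and are not touched by this. The gap of 15-25 days between last class and scans is an assumed scenario (credits used at exactly two per week from Day 8), not something the plan states. The change is worth making before follow-up begins, because a missed measurement cannot be recovered at analysis.

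**What to change.** 1. Set one calendar window at the end of the 12-week course for the three tests in every patient with a baseline, whatever the attendance. It could be the last scheduled week up to Day 91, or a window matched to Day 92-99.
2. Use the same setting and the same medication state as at baseline for all patients. Do not send only low attenders to the medical-centre visit. That visit includes off-drug UPDRS-III, and its MRI follows a 16-hour washout, while no washout is stated for the exercise-site tests. A site and medication difference would then follow attendance.
3. Record the actual test dates and the days from last class to each follow-up assessment, including MRI and PET.
4. Separately, reconcile the class schedules (20 credits at roughly two per week, twice weekly, and 12 once-weekly classes), and define completion of the exercise programme against Day 92-99. Which schedule applies is for the sponsor to state.

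The cost is a protocol wording and schedule change, and calling back some early stoppers for a short assessment. A window in the last course week adds no visit for patients still attending. Matching Day 92-99 aligns better with imaging but, if the exercise site is kept, means a return after the course for everyone.

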2.3 END OF STUDY DEFINITION

PD cohort

A participant is considered to have completed the study if he or she has completed both baseline and follow-up assessment phases of the study, as well as attended at least 1 of the community-based exercise classes.

The end of the study is defined as completion of the last visit or procedure shown in the SoA in the trial globally.

Healthy cohort

A participant is considered to have completed the study if they have completed the BEST.

3 STUDY DISCONTINUATION AND PARTICIPANT DISCONTINUATION/WITHDRAWAL

[figure not shown]
3.1 PARTICIPANT DISCONTINUATION/WITHDRAWAL FROM THE STUDY

Participants are free to withdraw from participation in the study at any time upon request.

An investigator may discontinue or withdraw a participant from the study for the following reasons:

- Significant study intervention non-compliance or lost to follow-up
- If any clinical adverse event (AE), laboratory abnormality, or other medical condition or situation occurs such that continued participation in the study would not be in the best interest of the participant
- Disease progression which requires discontinuation of the study intervention
- If the participant meets an exclusion criterion (either newly developed or not previously recognized) that precludes further study participation
- Participant unable to complete follow-up assessments.

The reason for participant discontinuation or withdrawal from the study will be recorded.

- 56. Fahn, S., & Elton, R. L. (1987). UPDRS program members. Unified Parkinson's disease rating scale. *Recent Developments in Parkinson's Disease*, *2*, 153-163.
- 57. Hughes, C. P., Berg, L., Danziger, W., Coben, L. A., & Martin, R. L. (1982). A new clinical scale for the staging of dementia. *The British Journal of Psychiatry*, 140(6), 566-572.
- 59. Reitan RM. The relation of the trail making test to organic brain damage. J Consult Psychol. 1955;19(5):393-4. PubMed PMID: 13263471.
- 62. [name], C.M. & Abeare, C.A. (2015). Brief Estimate of Seconds Test (BEST). Unpublished instrument.
- 63. Simon, J. R. (1969). Reactions towards the source of stimulation. Journal of experimental psychology, 81, 174–176.

1 STATISTICAL PLAN

1.1 AIM 1

Aim (1). To quantify the relationship between CNS lymphatic measures and beta-amyloid burden.

- Hypothesis (1A). Glymphatic flow and lymphatic collector velocity inversely correlate with beta amyloid measured from 18F-florbetapir PET in older adults with Parkinson's disease.
- Exploratory Hypothesis (1B). In Parkinson's subjects matched for age and sex, glymphatic flow and betaamyloid burden will be worse in patients with versus without mild cognitive impairment (MCI).

A.1.1 Experiment. We will enroll participants with idiopathic Parkinson's disease (n=32; age range=55- 80 years), equally distributed and matched for age and sex between groups with (n=16) and without (n=16) mild cognitive impairment. These populations provide a cohort to evaluate the potential relationship between glymphatic flow and beta-amyloid burden, given the elevated risk of beta-amyloid accumulation associated with both conditions. These patients will form a cohort to be assessed before and after a community-based exercise intervention. Participants will be recruited from Vanderbilt University Medical Center Neurology's Behavioral and Cognitive and Movement Disorder Clinics by Drs. [name] and [name]. Potential participants will undergo a neurological and neuropsychological examination to characterize their medical and neurobehavioral status. Patients will have medical and motor presentation indicated for the community-based exercise program. Those patients with clinically-defined MCI, will be without evidence of vascular cognitive impairment, primary mood disorder, Lewy body disease, or comorbid medical condition that could contribute to cognitive symptoms (e.g. pulmonary, hematologic, metabolic, or vitamin deficiency).

A.1.1.1. Clinical and neuropsychological examination. All potential participants will undergo baseline clinical and neuropsychological examination to determine eligibility, categorize MCI status, and provide quantification of neurocognitive functioning and neuropsychiatric symptomatology. The neuropsychological examination protocol will consist of memory measure (i.e., the Hopkins Verbal Learning Test – Revised [HVLT-R], consisting of Learning, Recall, and Recognition subcomponents). We will also administer three executive functioning measures (i.e., Trail Making Test – A & B57, Verbal Fluency [FAS], Stroop]), to facilitate exploratory analyses. To evaluate sleep disturbance symptomatology, PROMIS – Sleep Disturbance (SD) and Sleep-related Impairment (SRI) short forms will be administered.

A.1.1.2. PET. A single administration of approximately 370 MBq (10 mCi) Florbetapir 18F, then a 10- minute PET acquisition (2 × 5 minute frames) approximately 50 minutes later will be performed. Images will be reconstructed using an ordered subset estimation algorithm (4 iterations, 16 subsets, with a post-reconstruction Gaussian filter of 5 mm), and corrected for scatter and attenuation. Images will be co-registered to the high spatial resolution T1-weighted image as we have performed previously and a mean cortical:cerebellar SUVr will be calculated as the primary parameter of interest. For exploratory evaluation, we will also record SUVr in bi-temporal, bi-occipital, bi-frontal, and biparietal lobes.

A.1.1.3. MRI. The following imaging and angiography sequences will be completed. We will apply our previously reported 3T methods (16-channel neurovascular coil) with the below 50 min protocol:

Anatomical imaging. T1-weighted (MPRAGE; spatial resolution=1.0x1.0x1.0mm3; 3D turbo-gradient-echo; TR/TE=8.2/3.7ms), and T2-weighted (FLAIR; spatial resolution=0.9x1.1x3.0mm3; turbo-inversion-recovery; TR/TI/TE=11000/2800/120ms) imaging, and intracranial (spatial resolution = 0.5x0.8x1.4mm3; 3D gradient

echo; TR/TE=23/3.5ms) and extracranial (spatial resolution=0.9x0.9x3.0mm3 ; 2D gradient echo; TR/TE=18.6/3.2ms) time-of-flight (TOF) MR angiography (MRA).

Microvascular hemodynamic compliance. A single-shot gradient echo echo-planar-imaging (EPI) scan (TE=30 ms), multiband-factor=3, isotropic spatial resolution=2 mm, SENSE-factor=2.5, and TR=1s will be acquired with whole-brain coverage. The scan will utilize a hypercapnic normoxic (5% CO2 / 21% O2 / 74% N2) stimulus. The stimulus will be administered through a tight-fitting non-rebreathing oxygen facemask from compressed gas cylinders (flow rate=12 L/min) with the following paradigm: 180s normocapnic normoxia / 90s hypercapnia repeated once, followed by 180s normocapnic normoxia. Heart and respiration rate, EtCO2, and FiO2 will be recorded.

CSF flow. 2D-Qflow measurements will be performed in the cerebral aqueduct. Venc=12 cm/s, spatial resolution = 0.5x0.5x4 mm3, field-of-view = 200x200x4 mm3, and 30 frames per heart cycle. Scan durations vary with heart rate, but are generally 2-4 min. Reproducibility has been determined by CSF flow velocity. The CSF flow velocity over the cardiac cycle measured using the proposed sequence. Error bars extend to all data from six health subjects. The insert shows the location of the cerebral aqueduct (blue) and slice placement (orthogonal to flow). Velocity sign indicates direction. ICC=0.81. repeating the flow measurements in six subjects. Background correction will be performed with a method previously developed for quantification of blood flow velocity in small perforating arteries.

Lymphangiography for lymph vessel visualization. 3D turbospin-echo with variable refocusing angle sweep=40-110°, driven equilibrium module, dynamic DANTE flip angle sweep=0–8°, TE=600/TR=2500ms, slices=80, spatial resolution=1x1x1mm3. We have shown that this method provides sensitivity to long T2 slow flow species, such as lymph, and we have evaluated this method for sensitivity to lateralizing lymphedema and MLD therapy.

Susceptibility weighted imaging (SWI) for identification of medullary veins. Whole-brain 3D turbo-gradientecho (TR/TE1/ Δ TE=31/7.2/6.2 ms; flip angle=17°) with spatial resolution=0.6x0.6x2 mm3 (slices=130) will be acquired with the same slice angulation as DTI.

Diffusion tensor imaging (DTI) for perivascular flow determination. Whole-brain 2D spin echo EPI (TR/TE=10000/60 ms) in 32 directions (2 mm isotropic spatial resolution) using sequential acquisitions with b=0 s/mm2 , b=1000 s/mm2 , and b=2000 s/mm2 .

Spin labeling for cervical LN perfusion. Spin labeling will be performed with an 11-ms hypersecant inversion (labeling) prepulse, followed by an inversion time range of 300 to 2400 ms in 300 ms increments, which will enable blood transit time and perfusion quantification. Other parameters: labeling=STAR; TE=11 ms; spatial resolution=2x2x2 mm3; averages=14.

A.1.2. Analysis and statistical plan.

A.1.2.1 Clinical and neuropsychological examination. MCI will be defined based on established clinical criterion of cognitive performance below 1.5 standard deviations compared to age-based normative expectations in the memory domain and/or the executive functioning domain, with a Clinical Dementia Rating (CDR) of 0 or 0.5, indicating cognitive dysfunction has not contributed to functional dependence for activities of daily living61, 62. The memory domain by determining the mean memory score across performance on the HVLT-R (i.e., Learning Trials 1- 3, Delayed Recall, Delayed Recognition). Similarly, an executive functioning domain will be determined by the mean score across the TMT (part B), Stroop, and Letter Fluency. Clinical analyses will be overseen by Drs. [name] and [name].

A.1.2.2. Image analysis. Analysis will be overseen by the PI and radiology Co-Is Drs. [name] and [name], who together have experience with all image types. Lymphatic spin labeling. Sequential images are acquired (A) without and (B) with magnetic labeling (adiabatic inversion of arterial water spins). Following labeling, blood water flows into LNs (C,D) and attenuates signal. The difference image is proportional to perfusion

(ml/100g/min), which can be quantified upon application of the flow modified Bloch equation (E: T2-weighted image of LNs; F: corresponding perfusion weighted signal). (G) The blood arrival (red) and lymph arrival (black) following labeling over six subjects and LNs (dimensions shown above). The blood signal peaks and decays first, with the magnitude indicating perfusion. The lymph signal peaks later, due to slower lymphatic flow; note that the lymphatic signal is detectable at such long delays due to the longer T1 of lymph (T1=3100 ms) relative to blood (T1=1650 ms).

Anatomical imaging. Gray and white matter volume will be recorded using FSL-FAST50. MRIs will be reviewed by radiology Co-I [name]. Infarct presence will be recorded if there is an ischemic lesion≥3 mm in diameter visible on FLAIR using established criteria of hyperintense on FLAIR and hypointense on T1 approaching CSF signal. [name] will also grade intracranial MRA for vasculopathy extent and abnormalities will be noted; the purpose is to ensure that all subjects have no radiological indicators of disease and no-to-mild (0-49%) stenosis.

Microvascular hemodynamic compliance. Data will be corrected for motion, baseline drift, and slice timing. Multiple regressors will be calculated for the data corresponding to the block hypercapnia paradigm but with different onset timing. This will allow for cross-correlation statistics, which describe the strength of the correlation between the regressor and the data, to be calculated on a voxel-wise basis for a series of regressors that are offset in time. The time shift for the regressor that provides the maximum correlation statistic will be chosen as the CVRDELAY as we have outlined previously, and the signal change normalized by the EtCO2 change at this point will be recorded as CVRMAX. Maps will be registered to a 2 mm atlas. The primary observables preserved for hypothesis testing will be the CVR metrics (CVRMAX and CVRDELAY) separately in gray matter parenchyma and CP.

CSF flow. Based on the standard deviation over time, voxels within the cerebral aqueduct showing significant flow above the noise floor will be recorded. Phase unwrapping will be performed. Net CSF flow will be determined by integrating the mean velocity over the heart cycle over all aqueduct voxels. The observable preserved for hypothesis testing will be the CSF flow velocity through the aqueduct.

Lymphangiography analysis. Lymph vessels will be visualized using a maximum intensity projection (MIP) of the 3D TSE data. The theory underlying flow-suppression in DANTE modules is that flowing spin magnetization is attenuated owing to a spoiling effect caused by flow along the applied gradient65. For slowly flowing spins, the spin magnetization is attenuated in a manner that depends on flow velocity. We will fit a model of signal decay as a function of flip angle, and we will record the mean lymphatic flow velocity in draining cervical vessels at the most distal level of the deep cervical LNs.

SWI analysis. Phase and magnitude data will be combined and a minimum intensity projection calculated. Images will be registered to DTI scans and used for region-of-interest selection.

DTI analysis. Data will be processed using FSL66, including motion- and eddy current-correction, and will be brain-extracted. Tensor eigenvalues and eigenvectors, as well as diffusivity (D) values will be calculated from the diffusion images, b-values, and b-vectors using dtifit. Radiology Co-I [name] will draw regions-of-interest where the lateral projections of the medullary veins (from SWI) are orthogonal to the projection and association fibers, which occurs at approximately the location of the lateral ventricles. Within these regions the diffusivity in x, y, and z (Dxx, Dyy, Dzz) and DTIALPS

score=mean(Dxx,proj,Dxx,assoc)/mean(Dyy,proj,Dzz,assoc) will be quantified67; the primary variable of interest will be bilateral DTI-ALPS score.

Spin labeling analysis. We will follow our previously reported procedures68 and utilize recentlyquantified 3T T1 and T2 LN values. Images will be corrected for motion, pair-wise subtracted, and the flow-modified Bloch equation will be applied to quantify perfusion in absolute units (ml/100g/min). Spin labeling images will be registered to the anatomical image, which will allow us to localize LNs. The primary outcome variable will be mean LN perfusion in cervical LNs.

A.1.3. Statistical concerns. Statistical analyses will be overseen by statistician Co-I [name]. Descriptive statistics, including means, standard deviations, and ranges for continuous parameters, as well as percent and frequency for categorical parameters, will be presented. Tests for normality and homoscedasticity will be made. To test Hypothesis (1A), Pearson or Spearman (depending on normality findings) will be applied to evaluate the relationship between glymphatic flow, measured as the DTIALPS score, and the cortical:cerebellar SUVr, measured from PET. As an exploratory analysis to understand whether the relationship is spatially dependent, correlation testing will be repeated using the regional SUVr measures and corrected p-values reported. Power calculations are based on preliminary data in six MCI subjects in which an inverse correlation (Spearman's alpha =-0.49) was found between SUVr and DTI-ALPS score. With a sample size of 32, we should have 82% power to detect a correlation of -0.49 with two-sided p<0.05. To test Exploratory Hypothesis (1B), we will apply a Student's t-test or Wilcoxon rank-sum test (depending on normality findings), to evaluate whether mean glymphatic flow, measured as the DTI-ALPS score, is different between age- and sex-matched participants with vs. without MCI. Motivation is based on our preliminary data, where we have observed a large effect size (Cohen's d=2.3) in DTI-ALPS score between age- and sex-matched subjects with vs. without MCI.

A.1.4. Impact. Results will for the first time evaluate how the proposed human CNS lymphatic system and levels of beta-amyloid burden are altered in Parkinson's disease. If confirmed, results will motivate the use of evaluating human CNS lymphatic dysfunction with proposed methods for understanding betaamyloid clearance disorders.

A.2. Aims (2). Quantify the glymphatic functioning and beta-amyloid burden response to 12 weeks of a community-based exercise course developed specifically for PD patients.

Exploratory Hypothesis (2A). Exercise treatment will result in improved glymphatic functioning. Exploratory Hypothesis (2B). Exercise treatment will result in a reduction of cortical beta-amyloid uptake. Exploratory Hypothesis (2C). The degree of improvements in glymphatic functioning and cortical beta-amyloid uptake in response to exercise therapy will be more significant in MCI versus non-MCI participants. D.2.1 Experiment. We will enroll the patients from Aim (1) (A.1.) all of whom are undergoing community-based exercise intervention to treat symptoms of Parkinson's.

A.2.1.1. Exercise intervention procedure. Following baseline assessment, all patients will participate in a community-based kick boxing group exercise class designed for those living with Parkinson's called "Rock Steady Boxing." Patients will complete 12 consecutive, 90-minute, once-weekly classes, then undergo follow-up assessment. Treatment compliance will be monitored by the collaborating exercise trainer. All participants, regardless of degree of treatment compliance will receive follow-up assessment. *A.2.1.2. Imaging procedure.* PET and MRI methods as outlined in A.1.1.2. and A.1.1.3. will be performed.

A.2.2. Analysis and statistical plan. Our main hypotheses are that after 12 weeks of once-weekly exercise treatment for PD, glymphatic functioning (per DTI-ALPS) will improve and beta-amyloid burden (per PET) will decline. We expect that degree of treatment compliance standards will moderate these changes. We will also explore whether scalar degree of treatment compliance relates to degree of change in our assessment modalities. Statistical analysis will be overseen by statistics Co-I [name] and the same considerations outlined in Aims (1) will be applied. To test Exploratory Hypothesis (2A), a paired Student's t-test or Wilcoxon signed-rank test, depending on normality findings, will be applied to determine if glymphatic flow (DTI-ALPS score) is increased after, relative to before, exercise intervention. To test Exploratory Hypothesis (2B), an identical

procedure will be applied to evaluate differences in SUVr pre vs. post exercise intervention and corrected pvalues will be reported. To gain additional information, a multiple linear regression will be performed using the change in glymphatic flow (DTI-ALPS score) as the dependent variable and degree of compliance and change in beta-amyloid burden as the independent variables. To test Exploratory Hypothesis (2C), we will perform these same comparisons separately for MCI and non-MCI subgroups. Aim 2 hypotheses are exploratory, given limited extant literature defining reliable effect sizes; however, one randomized study (n = 33) demonstrated a 30% divergence in mean plasma levels of a CSF beta-amyloid marker between exercise (-6%) and non-exercise participants (+24%) with MCI. Thus, with the proposed sample size of 32 (each with a measurement before and after intervention), we should have at least 80% power to detect a significant difference in mean DTI-ALPS score pre- vs. post-exercise with at least 80% power and two-sided Type I error=5%. We should also have sufficient power to include two independent variables in the regression model. *A.2.3. Impact.* Results will provide evidence of how CNS lymphatic and beta-amyloid properties adjust in response to regular vigorous exercise in a PD sample.

A.3. Aim (3). Evaluate the degree to which neuroimaging-based response to exercise mediates clinical improvement in neurocognitive functioning and neuropsychiatric symptomatology.

Hypothesis 3.A. Neurocognitive functioning will improve following completion of the exercise intervention. Exploratory Hypothesis (3.B.). Sleep disturbance symptoms will diminish following completion of the exercise intervention.

Exploratory Hypothesis (3.C.). The degree of change glymphatic function and cortical beta-amyloid uptake in response to exercise therapy will be correlated with the degree of improvements in neurocognitive functioning.

Exploratory Hypothesis (3.D.). The degree of change glymphatic function and cortical beta-amyloid uptake in response to exercise therapy will be correlated with the degree of improvements in sleep disturbance symptomatology.

